## Section G: Sample Size/Data Analysis

### G1. Sample Size

How many subjects (or specimens, or charts) will be used in this study?

Local: 188 Worldwide: 188

Please indicate why you chose the sample size proposed:

In a retrospective IRB approved study, the peak pain scores in the PACU were  $2.8 \pm 2.9$  in the group receiving systemic analgesia without a regional block. A group size of 34 would have an 80% power of detecting a clinically relevant difference in the peak pain scores of 2 at the 0.05 level of significance, assuming the same SD in pain scores in the treatment group. We will recruit 40 patients in each group to allow for dropouts and incomplete data. This group size would

have a 90% power of detecting a 75% increase in time to first analgesia in the regional anesthesia group compared to the IV analgesia group, based on the retrospective study.

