The time taken to place the block will be recorded from the time the ultrasound probe is first placed on the child until completion of local anesthetic injection. The observer collecting postoperative data will not be present when the block is placed, and a band-aid will be placed over the supraclavicular fossa in all patients to maintain blinding of the observer to the group assignment. During the operation patients can receive intraoperative fentanyl, 1 mcg/kg IV at a time, if the attending anesthesiologist believes it is clinically indicated. At the end of the operation, anesthetic gases will be discontinued while the patient breathes 100% oxygen. The trachea will be extubated when the patient responds to commands, and the child will then be taken to the Post Anesthetic Care Unit (PACU) in keeping with standard practices. A validated pain scale (verbal rating scale where 0 = no pain and 10 = worst possible pain ever) will be used throughout to assess the severity of pain in the postoperative period. In keeping with current practice, patients with pain scores >4 will be treated with morphine 0.05mg/kg IV at 10 minute intervals until the score is below 4. Oral acetaminophen with hydrocodone (Lortab elixir 0.15mg/kg hydrocodone) will be administered to children for pain scores between 2-3. Supplemental oxygen, rescue antiemetic and antipruritic drugs will be administered in keeping with standard practices of TCH and the clinical judgment of the Attending Anesthesiologist. The duration of supplemental oxygen therapy, any medication administered and complications (side effects such as nausea, vomiting, itching, respiratory depression, prolonged awakening) will be recorded on the case report form.

The blinded observer will record pain scores within 15 minutes of arrival in the PACU and at 30 minutes, 1,2,6,12,24, and 48 hours after arrival in the PACU. If the child is sleeping at this time, the scores will be recorded when awake. The observer will also document any additional medication, the dose and the time given.

Prior to discharge home, parents will be educated on use of the 0-10 pain scale and given a diary to keep an accurate record of postoperative pain issues through the study period. The goal is to capture maximum pain scores at rest and with movement. Patient and parental satisfaction with pain management and with the global perioperative experience will also be graded on a numeric scale 0-10 scale.

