## G2. Data Analysis

Provide a description of your plan for data analysis. State the types of comparisons you plan (e.g. comparison of means, comparison of proportions, regressions, analysis of variance). Which is the PRIMARY comparison/analysis? How will the analyses proposed relate to the primary purposes of your study?

The primary endpoint of the study will be the peak or maximum pain score in the postoperative period. The secondary endpoints in the study will include (1) Opioid consumption in morphine equivalents (2) Time to first analgesia request (3) Time to achieving discharge readiness (4) Incidence of side effects such as vomiting, respiratory depression, itching, dysphoria, compartment syndrome (5) Patient and parental satisfaction. In order to keep the statistical analysis robust, we will also examine the differences in subjects who did or did not return the diaries regarding: a. group assignments b. age c. gender d. ASA physical status e. duration of surgery f. intraoperative opioids medications g. time of the PACU stay h. mean and peak pain scores and i. recorded opioid consumption in the PACU before discharge. These are known factors k that affect postoperative pain and failure to show a difference in these factors may suggest that the missing 48 hour data can be considered to be missing at random. We will also examine the PACU pain and opioid consumption data(first 2 hr after surgery) for all cases and separately for cases where the diaries were returned with the 48 hour data. If the conclusions regarding the secondary endpoints of pain in the PACU were not altered and the known factors affecting postoperative pain did not differ between those who did and did not return the diaries, it may suggest the conclusions are still robust. Our current plan will be modified to include not only daily phone calls from researchers, but Epic Mychart as well for protected email communication to better gather data.

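### G1 gives the sample size as 188 but justifies only 80 (40 per group), and nothing in the document derives 188 or reconciles the two figures

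*Combined protocol and SAP*

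**What the plan says.** Section G1 of the combined protocol and SAP gives the number of subjects as "Local: 188 Worldwide: 188". The next prompt on the form asks why that size was chosen, and the reply supports a different one:

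- The SD comes from earlier data: "In a retrospective IRB approved study, the peak pain scores in the PACU were" 2.8 ± 2.9 with systemic analgesia and no block.
- From that, "A group size of 34 would have an 80% power of detecting a clinically relevant difference" of 2 points at the 0.05 level, assuming the same SD in the block group.
- Recruitment is then set: "We will recruit 40 patients in each group to allow for dropouts and incomplete data".
- The same group size is said to "have a 90% power of detecting a 75% increase in time to first analgesia" for the block group, again from the retrospective study.

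F2 randomizes 1:1 into two groups. F1 describes a single-center study, and the local and worldwide counts are equal, so no other site can supply the difference. G2 defines the outcome: "The primary endpoint of the study will be the peak or maximum pain score in the postoperative period". F2 schedules scores within 15 minutes of PACU arrival and "at 30 minutes, 1,2,6,12,24, and 48 hours after arrival in the PACU".

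**The concern.** The two figures sit a few lines apart in current text and cannot both be the planned size. Forty per group already includes the allowance for losses, so 188 is not the same plan with attrition added. Neither power statement refers to 94 per group.

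The planned number fixes when recruitment ends and what the trial can detect. With two candidates and no described interim or stopping rule to settle the matter, stopping at 80 could be read as completion or as early termination, and continuing to 188 could be read as the plan or as over-enrolment.

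There is also a question of exposure. E1 classes the study as above minimal risk with a prospect of direct benefit, and the participants are children. If 188 is the real target, 54 more children per arm are enrolled than the justification covers. Section I says the IV group carries no added risk, so any added research risk falls on the block arm.

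**Working it through.** **Inputs.** From G1: difference 2 points; SD 2.9 in both groups; alpha 0.05; 34 evaluable and 40 recruited per group; total on the form 188. From F2: two groups, 1:1. G1 does not say whether alpha is one- or two-sided. Two-sided reproduces the plan's figure and one-sided does not (it gives 26 per group), so two-sided is used throughout.

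**Step 1: reproduce the plan's figure.** With the normal approximation, n = 2(1.960 + 0.842)² × 2.9² / 2² = 33.0, rounded up to 34. The t-test solution (noncentral t) is 33.99, again 34. The 34 per group is correct. Going from 34 to 40 implies a loss allowance of 1 − 34/40 = 15%.

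**Step 2: compare totals.**

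- Justified: 2 × 40 = 80.
- Stated: 188, so 188/2 = 94 per group.
- Gap: 188 − 80 = 108 children, or 94 − 40 = 54 per group.
- Ratio: 188/80 = 2.35.

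**Step 3: power and detectable difference at each size.** Two-sample t-test with noncentrality 2 / (2.9 × √(2/n)) and 2n − 2 degrees of freedom:

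| n per group | Power for 2 points | Difference detectable with 80% power |
|---|---|---|
| 34 | 80.0% | 2.00 |
| 40 | 86.1% | 1.84 |
| 94 | 99.7% | 1.19 |

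**Step 4: can 94 per group be reached from G1's inputs?**

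- *Higher power:* 90% needs 46 per group, 95% needs 56 and 99% needs 79.
- *Nonparametric test:* dividing 33.99 by a relative efficiency of 0.955 or 0.864 gives 36 or 40 per group.
- *Attrition:* leaving 34 of 94 means losing 1 − 34/94 = 64%; leaving 40 of 94 means losing 1 − 40/94 = 57%. No loss rate is stated.
- *Secondary endpoint:* the 90% claim for time to first analgesia is attached to the 40-per-group size. G1 gives no mean, SD or event rate for it, so it cannot be checked at either size.

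None of these routes arrives at 94.

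**Step 5: a limit on the power figures.** The SD of 2.9 describes peak pain in the PACU. The primary endpoint is the peak over the postoperative period, with scores to 48 hours, and the documents give no SD for that window. Taking SDs of 2.5 to 3.5 purely as an assumption, power for 2 points is:

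| Assumed SD | n = 40 | n = 94 |
|---|---|---|
| 2.5 | 94.2% | above 99.9% |
| 3.5 | 71.4% | 97.4% |

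The inconsistency does not depend on this range. It shows only that restating power at a single N also requires naming the window.

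**The case against.** The strongest reply is that 188 is an updated count above a rationale that was not updated. G2 discusses unreturned diaries, asks whether "the missing 48 hour data can be considered to be missing at random", and says the current plan will be modified to gather data better. That fits a form edited over time, in which case the defect is a stale justification and there are not two live targets. This may be what happened. But G2 gives no non-return rate and no sample size, and the remedy it names is phone calls and portal messages. If diary loss is the reason for 188, G1 has to say so.

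A second reply is that subjects consent before assignment, so the form's count could exceed the number randomized. The document does not say this, and it would hardly account for 108 children.

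Third, inference is not badly harmed: on the plan's PACU inputs neither size is underpowered for 2 points. That is right. The case rests on the unclear end of recruitment and the mismatch between stated size and stated power, and not on lost power.

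Fourth, the 54 extra block-arm children are not all newly exposed. Section C reports more than 50 such blocks in this population within six months, Section I calls the added risks low and lists possible benefits, and H1 puts the risk no higher than for other patients having this block at the hospital. This stands: 54 is an upper bound on added exposure. It does not supply a derivation for 188.

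Finally, the SD window is a separate matter that would remain if G1 said 80 in both places. That is fair, and it is used here only as a caveat on the power figures.

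**Conclusion.** The concern holds and needs correcting before the sample size can be relied on. G1 states 188 and justifies 80, a factor of 2.35 and a difference of 108 children, and nothing else in the document closes the gap. The plan's 34 per group is arithmetically sound; the fault is the unexplained total.

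The counts follow from the text alone. The power figures assume a two-sided 0.05 t-test with SD 2.9 in both groups and apply to peak pain in the PACU. Why 188 was entered is not known from the documents.

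**What to change.** In G1, state one total in both places and show how it was derived. If the reason for 188 is loss to follow-up or unreturned diaries, give the assumed rate and the calculation. At that total, restate:

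- the power for peak pain, naming the window from which the SD comes (PACU or the whole postoperative period);
- the power for time to first analgesia, with the retrospective inputs it uses.

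The cost is wording and recalculation in G1, with no new visits or data items. The edit itself adds no patients. Which total is right is for the investigators to settle, and that choice determines whether 80 or 188 children are enrolled.

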## G2. Data Analysis

Provide a description of your plan for data analysis. State the types of comparisons you plan (e.g. comparison of means, comparison of proportions, regressions, analysis of variance). Which is the PRIMARY comparison/analysis? How will the analyses proposed relate to the primary purposes of your study?

The primary endpoint of the study will be the peak or maximum pain score in the postoperative period. The secondary endpoints in the study will include (1) Opioid consumption in morphine equivalents (2) Time to first analgesia request (3) Time to achieving discharge readiness (4) Incidence of side effects such as vomiting, respiratory depression, itching, dysphoria, compartment syndrome (5) Patient and parental satisfaction. In order to keep the statistical analysis robust, we will also examine the differences in subjects who did or did not return the diaries regarding: a. group assignments b. age c. gender d. ASA physical status e. duration of surgery f. intraoperative opioids medications g. time of the PACU stay h. mean and peak pain scores and i. recorded opioid consumption in the PACU before discharge. These are known factors k that affect postoperative pain and failure to show a difference in these factors may suggest that the missing 48 hour data can be considered to be missing at random. We will also examine the PACU pain and opioid consumption data(first 2 hr after surgery) for all cases and separately for cases where the diaries were returned with the 48 hour data. If the conclusions regarding the secondary endpoints of pain in the PACU were not altered and the known factors affecting postoperative pain did not differ between those who did and did not return the diaries, it may suggest the conclusions are still robust. Our current plan will be modified to include not only daily phone calls from researchers, but Epic Mychart as well for protected email communication to better gather data.

Descriptive statistics will be used for each group. The peak and mean pain scores, age, weight, opioid consumption, time to first analgesia and discharge readiness and satisfaction scores will be compared between the two groups using Students t test if the data is normally distributed, and nonparametric tests if the data are skewed. A Fisher's exact test or a Chi Square test with Yates correction will be used to compare the number of patients in each group with side effects as listed above. P values of <0.05 will be considered to be statistically significant.

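### Section G1 gives two incompatible trial sizes (188 in total, and 40 per group), and its 80% power rests on a PACU standard deviation that is not supported for the longer primary endpoint

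*Combined protocol and SAP*

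**What the plan says.** **Trial size (G1. Sample Size).** The entry for the number of subjects is "Local: 188 Worldwide: 188". The justification below it reads "A group size of 34 would have an 80% power of detecting a clinically relevant difference in the peak pain scores of 2". Alpha is 0.05. The recruitment figure follows: "We will recruit 40 patients in each group to allow for dropouts and incomplete data". F2. Procedure specifies 1:1 randomization.

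**Source of the SD (G1).** The variability input is a retrospective study in which "the peak pain scores in the PACU were" 2.8 ± 2.9 in children given systemic analgesia without a block. The block arm is handled by "assuming the same SD in pain scores in the treatment group".

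**Primary endpoint (G2. Data Analysis).** "The primary endpoint of the study will be the peak or maximum pain score in the postoperative period". No end time is given. Later in G2, PACU data are described as covering the first 2 hours after surgery, and PACU pain is treated as secondary: "If the conclusions regarding the secondary endpoints of pain in the PACU were not altered". G2 also asks whether "the missing 48 hour data can be considered to be missing at random".

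**Follow-up.** The primary hypothesis in Section D concerns pain scores throughout the study. F2 schedules scores from PACU arrival to 48 hours. It also provides a home diary, meant to record maximum pain, with entries at 12, 24 and 48 hours, and telephone calls on postoperative days 1 to 3.

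**The concern.** The two sizes cannot both be the enrolment target. One is 2.35 times the other (188/80), and both stand in the section meant to justify the number. The trial is classed as greater than minimal risk and enrols children, so the number to be exposed and the reason for it should be clear from G1.

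The SD raises a separate question. The peak over a longer window is a different variable from the peak over roughly the first 2 hours. A child's maximum can only stay the same or rise as the window lengthens, but the spread between children can move either way. The documents give no SD for the longer window and no argument for carrying the PACU value over.

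The two matters are linked. At 34 evaluable per arm, a moderately larger SD would noticeably reduce power. With about 79 evaluable per arm it would make little difference. How much the SD matters therefore depends on which enrolment figure is in force.

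**Working it through.** **Inputs.** From G1: difference 2, SD 2.9 in both arms, alpha 0.05, 34 per group for power, 40 per group recruited, 188 in total. From F2: 1:1 allocation. G1 does not say whether the test is one- or two-sided. Two-sided is used here because it reproduces 34; a one-sided test would need only 26.

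**1. Reproduce G1.**
- Normal approximation: n per arm = 2 × (1.960 + 0.842)² × 2.9² / 2² = 33.0, just above 33, so 34 after rounding up.
- Two-sample t-test (noncentral t): n = 33.99, so 34. Power at 34 is 80.0%.

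The stated figure is right for its inputs.

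**2. Compare the two sizes.**
- 40 × 2 = 80, and 188 − 80 = 108 children unexplained.
- Loss implied by 40 recruited and 34 evaluable: 1 − 34/40 = 15%.
- If 188 were enrolled to leave 80, the loss would be 1 − 80/188 = 57%. No section mentions a loss of that order.
- 188/2 = 94 per arm. With difference 2 and SD 2.9, power is 99.7%. The difference detectable with 80% power would be 1.19 points, not 2.

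G1's inputs therefore do not lead to 188.

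**3. Put both designs on an evaluable basis.** G1's 80% applies after losses, so the comparison should too. Applying the same 15% to 94 gives 94 × 0.85 = 79.9, taken as 79.

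**4. Power over a range of SDs.** Power comes from the noncentral t with noncentrality (2/SD) × √(n/2) and 2n − 2 degrees of freedom. For example, at n = 34 and SD 2.9 the noncentrality is 0.690 × 4.123 = 2.84. The SDs of 2.5 and 3.5 are assumptions, since the documents give no value for the longer window.

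| Evaluable per arm | SD 2.5 | SD 2.9 | SD 3.5 |
|---|---|---|---|
| 34 (40 enrolled) | 90% | 80% | 64% |
| 79 (94 enrolled) | 99.9% | 99.1% | 94.6% |

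The evaluable number per arm needed for 80% power is 26, 34 and 50 at these three SDs.

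**5. Window of the primary endpoint.** Four things point to 48 hours rather than the PACU: the hypothesis in Section D, the scoring schedule and diary in F2, the concern in G2 about missing 48-hour data, and the secondary status G2 gives to PACU pain. No sentence fixes the end of the window.

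**The case against.** The strongest reply is that G1 is clear about its power statement. The 80% is tied to 34 per group, 40 is explained as an allowance for losses, and the arithmetic is right. All of that stands. What is unclear is the enrolment target, not the n behind the 80%.

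It can also be said that borrowing the best available SD is ordinary planning practice, and that the power sentence refers simply to peak pain scores, which is compatible with the endpoint in G2. This stands too. The criticism is limited to an SD carried over from a shorter window without comment. Nor is it a weakness peculiar to this plan that 34 leaves nothing to spare at SD 2.9: any minimum sample size has no slack at its own planning values.

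The 48-hour window is fairly consistent across sections, and the call on postoperative day 3 may only collect data already recorded. Stating the window is a clarification, and would not by itself carry this point.

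A reader might infer that the trial is underpowered for its primary endpoint. The documents do not support that. They give no SD for the longer window, a smaller SD would raise power, and at the 188 size power stays high across the range examined. A reader might equally infer that 188 settles the matter. It would only if 188 is the real target, and the same section says 40 per group.

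**Conclusion.** The point holds in two parts. The first carries most of the weight: G1 contradicts itself on trial size (188 against 80), and the written justification supports only the smaller number. The second is that power for the primary endpoint is not established, because the SD of 2.9 describes PACU peak pain while the primary endpoint is the postoperative peak, apparently to 48 hours. The 80% is not shown to be too high or too low.

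Within the assumed SD range of 2.5 to 3.5, power runs from 90% down to 64% at 34 evaluable per arm, and from 99.9% down to 94.6% at about 79. These figures assume a two-sided t-test at 0.05, a true difference of 2 points, equal SDs and a 15% loss in either design. The textual facts and the arithmetic are certain; the effect on actual power is not. This should be corrected.

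**What to change.** In G1:
- State one enrolment total with its derivation, and the expected evaluable number per arm. If 188 is intended, give the reason for it; if 80 is intended, correct the entry.
- Say that the SD of 2.9 is borrowed from PACU peak scores.
- Restate power for 2 points at the evaluable number, over SDs of 2.5 / 2.9 / 3.5: either 90% / 80% / 64% at 34 per arm, or 99.9% / 99.1% / 94.6% at about 79. Do not quote power at 40 or 94, which would assume no losses.

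In G2, state the window of the primary endpoint (PACU arrival to 48 hours, if that is what is intended).

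The cost is a few sentences, and a power statement that becomes a range instead of one figure. No new data, larger enrolment or change of endpoint is needed.

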## Section C: Background Information

Supracondylar fracture of the humerus is a very common traumatic injury in pediatric orthopedic practice, accounting for more than half of all elbow fractures and roughly 33% of all pediatric limb fractures. They are classified into 3 types depending on the degree of displacement. Type 1 fractures have no or minimal displacement and can be managed with splinting and casting. However, surgical manipulation via closed reduction and percutaneous pinning with cast placement is usually required in type 2 supracondylar and lateral condyle fractures. Significant tissue interposition in type 3 supracondylar fractures may require an open operation for fracture reduction. These procedures all require general anesthesia, but postoperative pain can delay discharge, increase anxiety, and decrease satisfaction by the patient and parent. In addition, the treatment of pain with parenteral opioids can be associated with side effects like nausea, vomiting, respiratory depression and dysphoria. In adults, regional anesthesia with brachial plexus nerve block provides excellent analgesia while avoiding the side effects of opioids. However, until recently these nerve blocks were not often placed in pediatric patients because of concerns that improper positioning of the needle would result in low success rates, potential injury and toxicity from local anesthetics. Surgeons are also extremely concerned that analgesia from nerve blocks would hinder early diagnosis of a compartment syndrome at the site of injury, increasing the potential for long term injury. Compartment syndrome has an incidence of 0.1-0.3% based on a recent retrospective analysis with the main factor on presentation being a poorly perfused extremity and absent pulses. There are no case reports confirming that this has occurred in children receiving regional analgesia. The recent development of ultrasound guided nerve blocks has permitted a more precise visualization of the needle position and spread of local anesthetics, thus increasing the success rate with lower doses of local anesthetic and reducing needle trauma. Supraclavicular and infraclavicular ultrasound guided blocks of the brachial plexus are relatively easy to perform and have been shown to decrease the time to first rescue analgesia in a retrospective case review. Over 50 brachial plexus blocks have been performed in this patient population during the last 6 months at the Texas Children's Hospital, with the other patients receiving IV analgesia. However, there are no prospective data to show the benefits of brachial plexus blockade over systemic analgesia in children with supracondylar fractures.

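### Age, named in the plan as a factor in postoperative pain, is significance-tested between randomized arms but not used to adjust the primary comparison of peak pain

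*Combined protocol and SAP*

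**What the plan says.** Section G2 defines the outcome: "The primary endpoint of the study will be the peak or maximum pain score in the postoperative period". For the analysis, peak pain, other outcomes and two baseline variables share one sentence: "The peak and mean pain scores, age, weight, opioid consumption, time to first analgesia and discharge readiness and satisfaction scores will be compared", and they "will be compared between the two groups using Students t test if the data is normally distributed, and nonparametric tests if the data are skewed". One threshold covers all of them: "P values of <0.05 will be considered to be statistically significant". No covariate-adjusted or stratified analysis is given for any endpoint. Section F2 describes 1:1 computer-generated allocation and mentions no stratification.

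Earlier in G2 there is a list of variables for comparing children whose diaries were returned with those whose diaries were not. It includes age, gender and ASA status, along with duration of surgery, intraoperative opioids and several PACU measures. Of this list the plan says: "These are known factors k that affect postoperative pain". Weight and fracture type are not in it. The list is used only for the question of missing diaries.

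Section G1 gives the design figures: "A group size of 34 would have an 80% power of detecting a clinically relevant difference in the peak pain scores of 2". Alpha there is 0.05. The variability input is stated as "assuming the same SD in pain scores in the treatment group", and it comes from a retrospective peak PACU score of 2.8 (SD 2.9).

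**The concern.** Two things are at stake.

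First, a significance test of age or weight between randomized arms tests a null hypothesis that is true by design. A small p value may be misread as failed randomization. A large one may be taken as reassurance while a prognostic imbalance remains in the treatment contrast. The plan does not say what would follow from either result.

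Second, the plan names baseline factors that it believes affect pain, intends to collect them, and leaves them out of the primary comparison. Section F1 admits ages 2 to 17, so age varies widely in this sample. If it is prognostic, adjustment narrows the interval for the treatment difference and removes the part of any chance imbalance that age explains. An adjustment added after the data are seen would look selective, so it belongs in the plan now.

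**Working it through.** **1. Reproduce the plan's figure.** Inputs from G1: difference 2, SD 2.9 in both arms, alpha 0.05 (taken as two-sided), power 80%.

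- Normal approximation: n = 2 × [2.9 × (1.960 + 0.842) / 2]² = 33.005, rounded up to 34.
- Noncentral t: n = 33.99, rounded up to 34. Power at 34 per arm is 0.800.
- A one-sided calculation gives 26 and does not match.

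The stated 34 per group is therefore the size for an unadjusted two-sided t test.

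**2. Validity of the unadjusted test.** With 40 per arm, no treatment effect and a covariate explaining a share R² of the variance (40,000 simulated trials), the t test rejected in 0.050 of trials at R² = 0.10 and 0.049 at R² = 0.30. Omitting the covariate does not inflate the error rate.

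**3. The baseline tests.** Each has a 5% chance of a spurious finding. For two independent tests the chance of at least one is 1 − 0.95² = 0.0975. Age and weight are correlated in children, so the chance lies between 0.05 and 0.0975.

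**4. What a non-significant imbalance can do.** At 34 per arm the standard error of a standardized mean difference is √(2/34) = 0.243. With a critical t of about 2.00 on 66 degrees of freedom, age can differ by about 0.48 SD and still pass the test. The resulting shift in the pain contrast is √R² × 2.9 × 0.48. At R² = 0.10 (assumed) this is 0.316 × 2.9 × 0.48 = 0.44 points, or 22% of the 2-point target.

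**5. Power after adjustment.** The documents give no R² for peak pain, so a range is assumed. The residual SD is 2.9 × √(1 − R²): 2.83, 2.75 and 2.59 at R² = 0.05, 0.10 and 0.20. Putting these into the t-test formula at 34 per arm gives 0.82, 0.84 and 0.88. Those values are too high, because they ignore the degrees of freedom spent and the variance added by chance covariate imbalance. Simulating the adjusted model itself gives:

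| Analysis, 34 per arm | R² = 0 | 0.05 | 0.10 | 0.20 |
|---|---|---|---|---|
| Unadjusted | 0.80 | 0.80 | 0.80 | 0.80 |
| One covariate (age) | 0.79 | 0.81 | 0.83 | 0.87 |
| Five covariate terms | about 0.77 | 0.79 | 0.81 | 0.85 |

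A five-term model loses power when R² is 0.05 or less, so the short model is the safer choice.

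**6. Dependence on the sample size.** G1 gives both 40 per group and a total of 188, an inconsistency separate from this point. At 40 per arm unadjusted power is 0.861; simulated adjustment for one covariate with R² = 0.10 gives 0.891. At 94 per arm unadjusted power is 0.997, which leaves almost nothing to gain.

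**The case against.** The strongest reply is that nothing here is an error. A 1:1 randomized comparison without covariates is unbiased, its error rate holds, and its sample size is consistent with it. Adjustment is an efficiency choice whose benefit rests on an R² that the documents do not supply. G2 already promises descriptive statistics by group, so dropping two p values is a reporting edit that cannot change the primary result. All of this stands, and it limits the weight of the point. It does not make the baseline tests informative, nor does it explain why a factor the plan considers prognostic is left out.

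A second reply is that a retrospective mean of 2.8 with SD 2.9 on a 0–10 scale suggests a floor and skewness, for which G2 provides nonparametric tests. A linear model that dropped this provision would be incomplete. That also stands, and the fix allows for it.

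A reader might infer three stronger claims:

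- **The plan ignores fracture type and weight although it says they drive pain.** It does not say so. Section C says of these fractures "They are classified into 3 types depending on the degree of displacement" and ties type to surgical management, not to pain. Weight is absent from the G2 list.
- **Fracture type is not recorded.** This cannot be shown. The case report form is not in the documents, and Section K says research data will include diagnoses and radiology findings from health records. What can be said is that fracture type is not named as a stratification or analysis variable. Eligibility is also restricted to one planned procedure, which narrows the range of severity.
- **The unadjusted result would be biased or invalid.** Step 2 of the working shows otherwise.

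**Conclusion.** The point holds as a matter of precision and interpretability, not validity. G2 tests age and weight between randomized arms to no purpose, and it leaves age, gender and ASA status out of the primary comparison after describing them as relevant to pain.

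The likely gain from adjusting for age alone at 34 per arm is 1 to 7 percentage points of power, if age explains 5% to 20% of the variance in peak pain. That range is an assumption. If age is not prognostic, power falls slightly, to about 0.79. If 188 children are enrolled, the power argument disappears, although adjustment would still remove chance imbalance in age and the baseline p values would still be uninformative.

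**What to change.** In G2:

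- Remove age and weight from the list of tested variables and describe them by arm without p values.
- Make the primary analysis a linear model of peak pain score on arm and age, with sex and ASA class as optional further terms fixed before the data are seen.
- Name in advance the version to be used if scores are skewed: robust standard errors, or a permutation or rank-based form of the same adjusted comparison.
- Keep the unadjusted two-group test as a supportive analysis.
- State that duration of surgery, intraoperative opioid and PACU variables will not be adjustment covariates. They arise after randomization and may be affected by the assigned treatment.

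Adding fracture type would be a judgment for the investigators, since the plan does not link it to pain.

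The cost is a few sentences in G2. Age, gender and ASA status are already needed for the diary comparison, so no new data are required for the core change. Statistically it costs one to a few degrees of freedom, with a small loss of power if the covariates turn out not to be prognostic.
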